14.2. Determination of Sample Size

For the primary analysis of peak workload, group sample sizes of 30 and 30 achieve over 99% power to reject the null hypothesis of equal means when the population mean difference is $\mu 1 - \mu 2 = 7.5 - 8.3 = 15.8$ with a standard deviation for both groups of 11.1 and with a significance level (alpha) of 0.05 using a two-sided two-sample equal-variance t-test.

Subjects who discontinue from the study may be replaced.

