	12. History, within the last 2 years, of alcohol abuse, significant mental illness, or physical opioid dependence
Food Journal requirement	While on study drug, subjects are recommended to avoid eating foods high in PUFAs. Subjects will keep food journals from screening through the completion of month 1 on study drug. After month 1, subjects will keep 2-week food journals prior to next scheduled onsite visit. Subjects (or parents/caregivers, as applicable) will have an initial call and as needed with the diet coach to discuss food journal completion requirements.
Prohibited Medications	Supplements that contain EPA or DHA are prohibited. Oil-based supplements like Fish oil, Cod Liver oil, Edible algae oil and Flax oil are also prohibited.
Statistical methods	Demographic data will be presented using descriptive statistics (e.g., mean, standard deviation, median, and range). Exposure to study drug and reasons for discontinuation will be tabulated. Safety variables will be tabulated and presented for all subjects who receive study drug or placebo capsules. Adverse events will be coded using the Medical Dictionary for Regulatory Activities (MedDRA). The incidence of treatment-emergent AEs will be presented by system organ class and preferred term. Adverse events will be presented by severity and relationship to

study drug. Changes from Baseline in clinical laboratory parameters and vital signs will be summarized across time. Shift tables will be provided for selected laboratory parameters. Physical examination results will be presented in listings.

Change from baseline (CFB) will be analyzed by comparing the change between treatment groups using a mixed model with repeated measures (MMRM). The MMRM will compare the estimated change from baseline between treatments for the primary endpoint. This analysis will assess whether there is a difference in estimated CFB between active and placebo groups at 11 months.

The primary analysis of percent change from baseline to 11 months in MVO2 as measured by CPET will use the ITT methodology and an MMRM methodology with a random slope and intercept for each individual.

All secondary and exploratory endpoints CFB values will be analyzed using the MMRM Responder analyses will be run on MVO2 (primary), GST, T1MW, Peak Workload, mFARS, and CGI-C (functional assessment). The PK of D2-LA, D2-ARA, H2-LA, and H2-ARA will be characterized in terms of minimum and maximum exposure at steady state.

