7.1. Primary endpoint

1. To demonstrate the efficacy of RT001 compared to placebo on the change of MVO2 in patients with FA through change from baseline to 11 months

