7.3. Secondary endpoints

- 1. To demonstrate the efficacy of RT001 compared to placebo on T1MW with change from baseline to 11 months
- 2. To demonstrate the efficacy of RT001 compared to placebo on the change of peak workload measured by CPET through change from baseline to 11 months

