9.3.4. Replacement of Subjects

Subjects who discontinue before enrollment is complete may be replaced in the study. Replacement subjects will be assigned unique subject numbers.

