Change from baseline (CFB) will be analyzed by comparing the change between treatment groups using a mixed model with repeated measures (MMRM). The MMRM will compare the estimated change from baseline between treatments for the primary endpoint. This analysis will assess whether there is a difference in estimated CFB between active and placebo groups at 11 months.

The primary analysis will use the ITT methodology and an MMRM methodology with a random slope and intercept for each individual. Due to the small sample size the model will be optimized by implementation of two risk scores (baseline and slope) that account for multiple baseline covariates in one variable. The risk scores will be derived from blinded data using the GST change from baseline values and generated using the baseline model covariates (excluding treatment and visit; baseline risk score) or the baseline model covariates*time interactions (slope risk score). The risk scores will be included as covariates in the model.

To calculate the baseline risk score, the GST change score is regressed on the covariates listed below. Individual coefficients for the baseline risk score are multiplied by individual covariate values and summed. A separate slope risk score is calculated for baseline covariates interacting with time.

The MMRM with primary outcome CFB value as the response variable will include the following covariates and fixed effects:

- baseline risk score:
 - baseline score for GST
 - age
- slope risk score:
 - baseline score for GST * time
 - age*time
- Time (continuous)
- Time by treatment interaction (time*treatment)
- baseline score for parameter of interest (if not in GST)
- site pooled by region (random effect)

Model assumptions will be evaluated. If the parametric assumptions are evaluated as inappropriate or violated, rank analogues will be advanced.

All secondary and exploratory endpoints CFB values will be analyzed using the MMRM described above. This analysis will assess whether or not there is a difference in estimated CFB values between treatment group and placebo at the 11-month model estimate using least squares means estimates from the MMRM model.

Speech measurement reporting will be analyzed by a third party vendor. A separate report will be provided.

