Responder analyses will be run on MVO2 (primary), GST, T1MW, Peak Workload, mFARS, and CGI-C (functional assessment). Responder analyses are performed to illustrate the clinical meaningfulness of the relationship between treatment differences and efficacy outcomes on a per

person basis. Responder analyses will be assessed at change from baseline cutoffs at the overall quartiles for each of the three variables. Patients who die or are unable to perform the test during the study will be counted as non-responders. Patients who do not complete will be carried forward using the last observation carried forward and the imputed value at the study endpoint will be used for the responder analysis.

In addition to summarizing the results for each relationship between individual clinical responses and treatment multiple clinical responses will also be correlated with treatment using the five GST component outcomes individually. Those who experienced the following combined clinical responses will be summarized in terms of counts and percent:

• Improvement or stabilization on at least 1, 2, 3, 4, and all of the 5 responder endpoints.

The PK of D2-LA and H2-LA will be characterized in terms of minimum and maximum exposure at steady state, based on a validated assay. The PK of D2-LA and H2-LA in RBC, D2-ARA, and H2-ARA also will be characterized in terms of minimum and maximum exposure at steady state; the validation of the assays to characterize these concentration values has not yet been validated.

Full details of planned analyses will be provided in a separate statistical analysis plan.

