14.3. Interim Analysis

One of two interim analyses may be performed. Retrotope will determine which interim, if either, to perform.

Interim analysis 1 using Month 4 data.

An interim analysis may be performed when all subjects have completed the Month 4 visit.

The Interim Analysis Committee (IAC) will report the following information to the steering committee, which will report the information to Retrotope management.

- The average within-treatment-group standard deviation of the change from baseline to Month 4 in CPET
- The average within-treatment-group standard deviation of the change from baseline to Month 4 in mFARS

That is, for CPET and for mFARS, the IAC statistician will calculate the within-treatment-group standard deviation of the change from baseline to Month 4 for each treatment group, and then calculate the average of the standard deviations of the two treatment groups.

The IAC will not report the mean change from baseline within treatment group and will not report the difference between the treatment groups in the mean change from baseline.

Retrotope may use this information on average within-treatment-group standard deviation to consider stopping the trial for futility or to consider sample size re-estimation.

The Interim Analysis Committee (IAC) will report the Pearson and Spearman correlation of the change in CPET with the change in mFARS at 4 months, and at the last available time point for each subject. Retrotope may use this information to re-order the primary and first secondary analyses.

There will be no alpha penalty for this interim analysis for the following reasons.

- 1. Only the average within-treatment-group standard deviations will be reported.
- 2. Neither mean change from baseline within treatment group nor the difference between the treatment groups in the mean change from baseline will be reported to Retrotope.
- 3. Retrotope will remain blinded to treatment assignments.

Interim analysis 2 using Month 11 data.

An interim analysis may be performed when approximately half the subjects have completed the Month 11 visit.

The Interim Analysis Committee (IAC) will report the following information to the steering committee, which will report the information to Retrotope management.

- The results of a futility analysis for the CPET endpoint
- The results of a futility analysis for the mFARS endpoint

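### The only power figure (over 99%) is for peak workload, a secondary endpoint; the primary endpoint MVO2 has no stated difference, SD or power

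*Combined protocol and SAP*

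**What the plan says.** Section 7.1 gives one primary endpoint: "To demonstrate the efficacy of RT001 compared to placebo on the change of MVO2 in patients with FA", measured at 11 months. Section 7.3 puts among the secondary endpoints: "To demonstrate the efficacy of RT001 compared to placebo on the change of peak workload measured by CPET". The synopsis has the same hierarchy, and the list of responder analyses in Section 14.1 again marks MVO2 as primary, with peak workload as a separate item.

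Section 14.2 is the only sample-size justification: "For the primary analysis of peak workload, group sample sizes of 30 and 30 achieve over 99% power to reject the null hypothesis". It uses group means of 7.5 and -8.3 (difference 15.8), an SD of 11.1 in both groups, two-sided alpha 0.05 and an equal-variance two-sample t-test. The synopsis repeats it. Neither place gives a unit or a source for the means and SD.

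Three other places bear on the point:

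- **Scale of the primary outcome.** The synopsis says: "The primary analysis of percent change from baseline to 11 months in MVO2 as measured by CPET will use the ITT methodology". Section 14.1 says: "The MMRM with primary outcome CFB value as the response variable will include the following covariates and fixed effects", where CFB is change from baseline.
- **Dropout.** No allowance is stated. Section 14.2 lets discontinued subjects be replaced without restriction, but Section 9.3.4 is narrower: "Subjects who discontinue before enrollment is complete may be replaced in the study".
- **Interim.** The optional Month 4 interim in Section 14.3 would report: "The average within-treatment-group standard deviation of the change from baseline to Month 4 in CPET". It does not say which CPET variable is meant.

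**The concern.** The trial presents over 99% as the power of its primary analysis, and that figure is the only stated basis for 60 subjects. Because it was worked out for a different endpoint, it says nothing about the chance of detecting an effect on MVO2. Renaming the endpoint in 14.2 would not repair it, since 15.8 and 11.1 are peak workload inputs. An IRB, the DSMB or a regulator would read the sentence as assurance about the primary endpoint. The gap also reaches the interim: an observed SD can drive sample size re-estimation only against a planned difference, and none exists for MVO2.

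**Working it through.** **Inputs.** n = 30 per arm, difference 7.5 - (-8.3) = 15.8, SD 11.1, two-sided alpha 0.05, equal-variance t-test (Section 14.2 and synopsis). The synopsis prints the second mean as negative. The minus sign is missing in the extracted text of 14.2, which I treat as a possible extraction loss and not as an error.

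**Step 1: reproduce the stated figure.**

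- Standardized effect: d = 15.8 / 11.1 = 1.423.
- Noncentrality: d × √(n/2) = 1.423 × √15 = 5.51, with 58 degrees of freedom.
- Power from the noncentral t distribution: 99.97%.

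The claim of over 99% is right for these inputs. About 12 per arm would give 90% and about 20 per arm 99%. At 27 per arm power is still 99.92%, so dropout hardly matters for peak workload.

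**Step 2: what 30 per arm requires of any other endpoint.** I solved the same power function for d. The 27/27 row assumes 10% loss (my assumption) with no contribution from those lost.

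| Per arm | 80% power | 90% power | 99% power |
|---|---|---|---|
| 30 | d = 0.736 | d = 0.851 | d = 1.126 |
| 27 | d = 0.777 | d = 0.899 | d = 1.189 |

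Under this t-test, 99% carries over to MVO2 only if its standardized effect is at least 1.126 / 1.423 = 79% of the one assumed for peak workload.

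**Step 3: range of MVO2 power at 30/30.** The documents give no d, so these values are assumptions.

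| Assumed d | 0.3 | 0.5 | 0.75 | 1.0 |
|---|---|---|---|---|
| Power | 21% | 48% | 82% | 97% |

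**Step 4: can the pilot fill the gap?** Section 6.4 reports median VO2 MAX changes after 28 days of -0.02 L/min (comparator) and 0.14 L/min (RT001), p = 0.116, with no SD. The group sizes and the test for this comparison are not stated. I assume 10 to 12 versus 6 subjects, as in the pilot's peak workload analyses, and a two-sided test. Then d = (statistic giving p = 0.116) × √(1/n₁ + 1/n₂):

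- 10 vs 6: 0.81 (normal) or 0.87 (t).
- 12 vs 6: 0.79 (normal) or 0.83 (t).

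Across these cases, t-test power is about 85% to 91% at 30/30 and 81% to 88% at 27/27. The 95% interval for d runs from about -0.2 to 1.9. It covers no effect and also covers 1.13, so the pilot does not settle the question. This is an illustration and not an estimate of the trial's power.

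**The case against.** The strongest reply is that this is a stale or incomplete justification and not a demonstrated weakness of the trial. N, design and analysis are untouched by the fix, and the pilot illustration gives conventional power. That is fair, and I do not claim the trial is underpowered. It does not rescue a sentence that presents 99% as the power of the primary analysis when it concerns another endpoint.

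Other points carry part of their weight:

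- **The planned model may do better than a t-test.** Section 14.1 specifies a covariate-adjusted repeated-measures model. If covariates explained 30% of the variance (an assumption), the unadjusted d for 99% power would fall to about 1.126 × √0.7 = 0.94; at 50%, to about 1.126 × √0.5 = 0.80. The model would also use the earlier visits of subjects who drop out. So the thresholds above are t-test thresholds only. The plan offers no calculation under its own model.
- **The interim could re-estimate sample size.** Section 14.3 permits this, and its CPET variable may well mean MVO2. But both interims are optional, CPET yields peak workload as well as VO2 MAX (Section 12.1), and no planned MVO2 difference exists to re-estimate against.
- **MVO2 and peak workload are correlated.** Section 6.4 reports cross-sectional correlation among the pilot measures. That gives neither the treatment effect on change in MVO2 nor its SD.
- **Full methods are deferred to a separate SAP.** The finding is limited to the supplied text. Section 14.2 is where the protocol justifies N, and it does so for another endpoint.

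**Conclusion.** The concern holds. The power sentence in 14.2 and the synopsis is attached to the wrong endpoint, and the supplied text contains no planning assumption for MVO2. The calculation is correct for the inputs printed; whether those inputs are sound for peak workload cannot be checked without a unit or source.

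Power for the primary endpoint is undetermined from the documents. Section 14.2 would need an MVO2 effect of about 0.74 SD for 80% power and 1.13 SD for its claim of 99%. These thresholds rest on an unadjusted t-test with all 60 subjects contributing. Power under the planned mixed model was not computed and may differ. An MVO2 difference and SD in natural units also cannot be given until percent and absolute change are reconciled, although a detectable effect in SD units can be given now.

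**What to change.** Keep N = 60 and make these changes:

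1. In Section 14.2 and the synopsis, relabel the peak workload figure as power for a secondary endpoint, with the unit and source of its means and SD.
2. Reconcile the synopsis (percent change) with Section 14.1 (change from baseline) so that MVO2 has one analysis scale.
3. On that scale, state the assumed MVO2 difference and SD with unit and source, and the resulting power at 30 per arm.
4. Reconcile the replacement rules in Sections 9.3.4 and 14.2, and give a dropout assumption consistent with the result.
5. If no defensible MVO2 assumption exists, state the smallest MVO2 effect detectable with 80% or 90% power instead. Under the t-test of 14.2 with 30 per arm, these are 0.74 and 0.85 SD.
6. Say in Section 14.3 which CPET variable the interim uses.

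The cost is protocol wording, plus the work of sourcing an MVO2 difference and SD. Design and analysis method stay as they are, apart from settling the scale. The sponsor would have to give up the over-99% claim for the primary analysis unless the MVO2 assumptions support it.

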14.3. Interim Analysis

One of two interim analyses may be performed. Retrotope will determine which interim, if either, to perform.

Interim analysis 1 using Month 4 data.

An interim analysis may be performed when all subjects have completed the Month 4 visit.

The Interim Analysis Committee (IAC) will report the following information to the steering committee, which will report the information to Retrotope management.

- The average within-treatment-group standard deviation of the change from baseline to Month 4 in CPET
- The average within-treatment-group standard deviation of the change from baseline to Month 4 in mFARS

That is, for CPET and for mFARS, the IAC statistician will calculate the within-treatment-group standard deviation of the change from baseline to Month 4 for each treatment group, and then calculate the average of the standard deviations of the two treatment groups.

The IAC will not report the mean change from baseline within treatment group and will not report the difference between the treatment groups in the mean change from baseline.

Retrotope may use this information on average within-treatment-group standard deviation to consider stopping the trial for futility or to consider sample size re-estimation.

The Interim Analysis Committee (IAC) will report the Pearson and Spearman correlation of the change in CPET with the change in mFARS at 4 months, and at the last available time point for each subject. Retrotope may use this information to re-order the primary and first secondary analyses.

There will be no alpha penalty for this interim analysis for the following reasons.

- 1. Only the average within-treatment-group standard deviations will be reported.
- 2. Neither mean change from baseline within treatment group nor the difference between the treatment groups in the mean change from baseline will be reported to Retrotope.
- 3. Retrotope will remain blinded to treatment assignments.

Interim analysis 2 using Month 11 data.

An interim analysis may be performed when approximately half the subjects have completed the Month 11 visit.

The Interim Analysis Committee (IAC) will report the following information to the steering committee, which will report the information to Retrotope management.

- The results of a futility analysis for the CPET endpoint
- The results of a futility analysis for the mFARS endpoint

Retrotope may use this information to consider stopping the trial for futility, to change the order of the primary and secondary endpoint, or to consider sample size re-estimation.

The Interim Analysis Committee (IAC) will report the Pearson and Spearman correlation of the change in CPET with the change in mFARS at 4 months, and at the last available time point for each subject. Retrotope may use this information to re-order the primary and first secondary analyses.

There will be no alpha penalty for this interim analysis for the following reasons.

1. The trial cannot be stopped for efficacy at this interim. It can only be stopped for futility.

Retrotope will remain blinded to treatment assignments.

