7.2. Key secondary endpoint

1. To demonstrate the efficacy of RT001 compared to placebo on an overall performance score based on a GST change from baseline to 11 months. The GST will be a combination of three endpoints (timed 1 minute walk test [T1MW], peak workload, and MVO2).

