7.4. Exploratory endpoints

To demonstrate the efficacy of RT001 on change from baseline at 11 months in clinical symptoms as measured by:

- 1. Modified Friedreich's Ataxia Scale (mFARS)
- 2. Fatigue Symptom Scale (items 2. 4. 7.9 of the total fatigue scale)
- 3. Clinician-rated Clinical Global Impression of Change (CGI-C)
- 4. Activities of daily living (ADL) elements of fatigue scale (items 5,6, 8, 10, and 11)
- 5. Patient Global Impression of Change (PGI-C)
- To evaluate the effects of RT001 on Visual Analogue Scale [VAS]
- To evaluate the effects of RT001 on speech measurements and Speech Assessment questionnaire
- To evaluate the effect of RT001 on T25FW
- To evaluate the effects of RT001 on FARS-Neuro
- To evaluate the effects of RT001 on FARS-ADL.

- To evaluate the effects of RT001 on SF-36
- To evaluate the effects of RT001 on the Neuro-QoL scales (Upper Extremity Function and Lower Extremity Function)
- To evaluate the effects of RT001 on the frequency of falls as reported in a fall diary and subject's fear of falling
- To evaluate the effects of RT001 on the Patient Global Impression of Change (PGI-C) Scale
- To evaluate the effects of RT001 on efficacy assessments after 4 months of treatment
- To evaluate the effects of RT001 on efficacy assessments after 8 months of treatment
- To evaluate the effects of RT001 on ejection fraction as reported in the Echocardiogram
- To evaluate the effects of RT001 on hypertrophy as reported in the Echocardiogram

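### Section 14.3 lets futility, re-sizing and endpoint order draw on exploratory mFARS and an unnamed CPET measure, and the key secondary GST is never an interim output

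*Combined protocol and SAP*

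**What the plan says.** **Hierarchy.** Section 7.1 gives the primary objective as "To demonstrate the efficacy of RT001 compared to placebo on the change of MVO2 in patients with FA through change from baseline to 11 months". Section 7.2 makes the GST key secondary: "The GST will be a combination of three endpoints", namely T1MW, peak workload and MVO2. Section 7.3 lists T1MW and peak workload as secondary. Section 7.4 puts mFARS first among the exploratory endpoints.

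**Interim plan (Section 14.3).** The sponsor decides which of two interims, if either, to perform.

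- Interim 1 takes place once all subjects reach Month 4. The committee reports the SD of the Month 4 change, averaged over the two arms, for CPET and for mFARS. The sponsor may use these to consider stopping for futility or re-sizing.
- Interim 2 takes place once about half the subjects reach Month 11. The committee reports "The results of a futility analysis for the CPET endpoint" and "The results of a futility analysis for the mFARS endpoint". The sponsor may use these to consider stopping, re-sizing or changing the endpoint order.
- Under both, the committee reports the correlation between CPET change and mFARS change, and "Retrotope may use this information to re-order the primary and first secondary analyses".

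**Sample size (Section 14.2).** The calculation opens "For the primary analysis of peak workload, group sample sizes of 30 and 30".

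**The concern.** An interim rule should act on the endpoints that carry the trial's claim. Here one of the two named variables is exploratory, and the other is the name of a test that yields two endpoints. The key secondary endpoint does not appear in Section 14.3 at all.

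Three decisions depend on this. Stopping is hard to reverse, re-sizing fixes the rest of the trial, and re-ordering changes which result is the main claim. Section 14.3 gives no thresholds or decision rules, so the named variables are the only constraint on how the sponsor uses the output. If they are clarified after interim results are known, the clarification will look data-driven.

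This is separate from whether the interim costs alpha, which is not considered here.

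**Working it through.** **1. Section 14.3 set beside Section 7**

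| Variable | Status in Section 7 | In Section 14.3? |
|---|---|---|
| MVO2 | Primary (7.1) | Not named; possibly meant by CPET |
| GST | Key secondary (7.2) | Absent |
| T1MW | Secondary (7.3) | Absent |
| Peak workload | Secondary (7.3) | Not named; possibly meant by CPET |
| mFARS | Exploratory (7.4) | Named in every type of output |

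**2. The re-ordering input.** Under Section 7, the primary and first secondary are MVO2 and GST. The input is the CPET-mFARS correlation. There are two readings. Either the order of MVO2 and GST may be changed on a correlation that involves neither GST nor any component of it on the mFARS side, or Section 14.3 treats mFARS as first secondary, which contradicts Sections 7.2 and 7.4. The text needs reconciling under both.

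**3. What CPET means.** Section 12.1 lists two CPET endpoints, peak workload and VO2 max (the abbreviation list defines MVO2 and VO2 max identically). In favour of MVO2, the synopsis describes the primary analysis as "percent change from baseline to 11 months in MVO2 as measured by CPET", Section 6.7 ties CPET to the primary endpoint, and the responder paragraph of Section 14.1 labels MVO2 primary. In favour of peak workload, Section 14.2, immediately before the interim section, calls it primary. A committee could choose either and comply.

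**4. The plan's own power figure.** Inputs from Section 14.2 and the synopsis: 30 per arm, difference 7.5 - (-8.3) = 15.8, SD 11.1, two-sided alpha 0.05.

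- Standardised effect: 15.8 / 11.1 = 1.42.
- Noncentrality: 15.8 / (11.1 × √(2/30)) = 15.8 / 2.866 = 5.51.
- Power, noncentral t with 58 df: 99.97%, in agreement with the stated figure of over 99%.

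That figure is for peak workload. No SD or effect is given for MVO2, so there is no planning value against which an interim MVO2 SD could be judged. Over an assumed range of standardised effects, power at 30 per arm is 21% at 0.3, 48% at 0.5, 86% at 0.8 and 97% at 1.0. A re-sizing decision is thus sensitive to the measure used, but the documents do not say where MVO2 lies in that range.

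**5. Scale.** Even if CPET means MVO2, the synopsis passage quoted in step 3 uses percent change, whereas Sections 7.1 and 14.1 use change. An SD or futility result differs between the two.

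**6. Would GST in place of mFARS repair the correlation?** No, because GST contains MVO2. Suppose, as an assumption (no weights are given), that GST is the mean of three standardised, mutually uncorrelated components. The covariance with MVO2 is 1/3 and the SD of the mean is √(3 × 1/9) = 0.577, so the correlation is 0.333 / 0.577 = 0.58 by construction. It would be a poor basis for choosing the order.

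**The case against.** The strongest reply is that MVO2 is measured by CPET, so the CPET endpoint can naturally be read as the primary. That stands. A reader might infer that the interim looks at the wrong variable in place of the primary; the documents show only that the variable is not pinned down.

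Three further points stand.

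- MVO2 and peak workload are two of GST's three components, so CPET output does inform GST in part. The supportable statement is that GST itself is never an interim output.
- At most one interim is run, and the sponsor may only consider acting. A reader might infer that an mFARS result would trigger stopping or that mFARS would be promoted; no such rule is written.
- Sections 14.1 and 14.3 leave thresholds open, and Section 14.1 defers full detail to a separate SAP, which may name the CPET variable. That would settle the ambiguity but not the conflict between Section 14.3 and Section 7 over mFARS and GST.

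A reader might also want to size the problem from the 28-day study in Section 6.4, where peak workload had p=0.008 and VO2 max p=0.116. Those figures do not support it. The first is a post hoc rank test on a modified ITT set (the ITT p is 0.021), the sample size and test for VO2 max are not restated, the duration is 28 days, not 11 months, and nothing there shows that a stopping decision would have been wrong.

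**Conclusion.** The point holds as a conflict between a stated rule and the stated hierarchy. An exploratory endpoint may inform stopping, re-sizing and endpoint order. The CPET measure is ambiguous between the primary and a secondary endpoint. The re-ordering input does not match the pair being re-ordered. These follow from the text alone.

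The consequence arises only if the sponsor elects an interim and acts on its output. No wrong decision is demonstrated, and no numerical size can be attached without assuming MVO2, GST and mFARS parameters that the documents do not give. The case for correcting it rests on the weight of the decisions involved and the need to settle the variables before any interim result is seen.

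**What to change.** In Section 14.3:

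- Replace CPET with MVO2 and state one scale, change or percent change, reconciling the synopsis with Sections 7.1 and 14.1.
- Base futility and re-sizing on MVO2. Label any mFARS output as supportive only.
- Delete the CPET-mFARS correlation as a ground for re-ordering MVO2 and GST, and do not substitute an MVO2-GST correlation (step 6 above).

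In Section 14.2 and the matching synopsis text, align the description of peak workload as primary with Section 7.

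If mFARS is really intended as first secondary, amend Sections 2 and 7 to say so before any interim data are seen.

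The cost is wording and less sponsor discretion at the interim. No additional subjects or data are needed.
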